6.6. Retrieval of Investigational Product

All participants who are prematurely discontinued from the trial will be encouraged to return to the research centre for a final evaluation, at which time all vaginal rings in the participant's possession should be retrieved. If the participant does not return her used or unused vaginal ring at this visit, it should be retrieved as soon as possible after this visit, either by the participant returning it to the trial staff, or by trial staff conducting a home visit.

For participants who are considered lost to follow-up and permanently discontinued from the trial, reasonable contact attempts will be made according to the locator information provided by the participant and local SOPs. Any used or unused vaginal rings that could not be retrieved will be documented in the source documents and applicable CRFs.

6.7. Investigational Product (IP) Accountability

The principal investigator or designee will be responsible for adequate and accurate accounting, handling, storage and dispensing of the IP. The IP will be stored safely and properly in a secure location with access available only to the principal investigator and designated trial personnel. IP and clinical supplies are to be dispensed only in accordance with the protocol. Accurate records of IP received from IPM, the amount dispensed to the participants, the amount returned by the participants, the quantity remaining at the conclusion of the trial and any wasted or expired IP will be maintained.

Unused and used rings not analysed for residual amounts of dapivirine will be destroyed according to IPM instruction and local regulatory requirements.

6.8. Concomitant Medications and Products

Prescription and non-prescription medications will be recorded on the source documents and applicable CRFs. Vaginal products and practices including the use of spermicides, intravaginal medication, douches, lubricants, tampons and female condoms may be used during the trial and will be captured. Further details will be provided in the SOM.

7. Adverse Events

7.1. Definition

An AE is any untoward medical occurrence during the course of a trial in a participant who received an IP at any dose, which does not necessarily have a causal relationship with the IP. An AE can therefore be any unfavourable and unintended sign (including an abnormal laboratory finding), symptom or disease temporally associated with the use of an IP, whether or not considered related to the IP. This definition includes inter-current illnesses or injuries and exacerbation of pre-existing conditions.

An *unexpected adverse event* is an adverse event, the nature or severity (intensity) of which is not consistent with the applicable product information (i.e. IB, package insert, or summary of product characteristics). Final determination of whether an event is considered *unexpected* will be made by the Sponsor, however, the investigator should be knowledgeable of the contents of the IB.

Whenever possible, the laboratory abnormalities should be considered in the context of the primary clinical diagnosis and should be reported as such (e.g. acute hepatitis with increased bilirubin). Clinically significant laboratory abnormalities will be considered AEs and graded for severity based on the Division of AIDS (DAIDS Table for Grading Severity of Adult and Pediatric Adverse Events) as appropriate.

Any condition occurring prior to enrolment will be reported as a pre-existing condition under Medical or Gynaecological History. All AEs occurring during the trial will be recorded in the source documents and applicable CRFs. All AEs will be reported and graded according to the latest version of the *DAIDS Table for Grading Severity of Adult and Pediatric Adverse Events* and *Female Genital Grading Table for Use in Microbicide Studies* (which will be provided to research centres in the SOM). A vaginal bleeding abnormality thought to be due to contraception, asymptomatic BV and asymptomatic candidiasis will not be reported as an AE for this trial.

If a unifying diagnosis is possible, the investigator should record a specific disease or syndrome rather than individual associated signs and symptoms. However, if an observed or reported sign, symptom, or clinically significant laboratory abnormality is not considered a component of a specific disease or syndrome by the investigator, it should be recorded as a separate AE.

All AEs will be monitored until resolution and/or the cause are identified, or until the investigator does not expect any improvement or worsening of condition/symptoms. If a SAE, urogenital AE or related AE remains unresolved at the participant's Exit Visit, the research centre investigator will make a clinical assessment with the IPM Clinical Physician to determine whether continued follow-up of the AE is warranted. All other AEs that are not serious, not urogenital and assessed to be unrelated to IP will be noted as ongoing at trial end if the outcome is not yet determined at the time of the exit visit.

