Based on information in the current IB⁵, across all completed Dapivirine Ring-004 trials (IPM 024, IPM 013, IPM 015, IPM 028 and IPM 034), the most commonly occurring TEAEs that were documented in at least 5% of participants in dapivirine versus placebo treated participants (n=259 using dapivirine rings and n=160 using placebo rings, respectively) were metrorrhagia (29.7% vs 24.4%), headache (15.1% vs 11.9%), gynaecological chlamydia infection (8.5% vs 13.4%), vaginal candidiasis (8.1% vs 7.5%), urinary tract infection (6.9% vs 8.8%), vaginal discharge (6.6% vs 6.3%), upper respiratory tract infection (5.8% vs 10.0%) and lower abdominal pain (5.4% vs 5.0%).

1.4.1.1. *Oral Dapivirine*

There have been 11 oral administration trials in which a total of 211 participants have been dosed with dapivirine. The maximum tolerated dose (MTD) established was 350 mg for a single dose, and for multiple doses, 300 mg b.i.d. for 14 days. There were no deaths during the clinical trials of oral dapivirine, and no trials were stopped for safety reasons. A total of 10 participants stopped dapivirine treatment prior to trial completion for safety reasons, 6 of whom stopped due to a clear dose-dependent increase in central nervous system (CNS) and gastrointestinal TEAEs, thereby establishing the MTD at 300 mg b.i.d. These TEAEs resolved within 1-2 days after discontinuation of use of oral dapivirine.

Adverse events documented in 5 or more participants (> 2%) after oral exposure to dapivirine were headache, dizziness, nausea, diarrhoea, fatigue, tremor, somnolence, flatulence, and vomiting. Most ($\geq 80\%$) of these TEAEs were Grade 1 or 2 (mild or moderate) and most ($\geq 80\%$) were considered to be related to dapivirine. Grade 3 (severe) TEAEs included headache, dizziness, injury, nausea, tremor, paraesthesia, disturbance in attention, abrasion, AST increased, ALT increased, polyuria, fever, diarrhoea, and vomiting. The increases in AST and ALT were transient and the Grade 3 increases in AST and ALT occurred in a single participant who received 50 mg oral dapivirine as a twice daily dose.

1.4.2. *Phase III*

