2.2. Trial Endpoints and Assessments

The primary endpoints are:

1. Safety
 - All Adverse Events (AEs) assessed by the investigator to be related to the Dapivirine Vaginal Ring-004
 - All Grade 3 and 4 AEs
 - All Serious Adverse Events (SAEs)
2. Adherence
 - Residual amounts of dapivirine in returned rings; and/or dapivirine concentrations in plasma and/or dapivirine concentrations in vaginal fluid

The primary endpoints will be assessed through:

1. Safety
 - All product-related AEs, Grade 3 or 4 AEs, SAEs, physical examination, gynaecological assessments, including pelvic/speculum examination, laboratory tests and other indicated investigations
2. Adherence
 - Determined dapivirine residual amounts in returned used vaginal rings and/or
 - Measured concentrations of dapivirine in plasma and/or
 - Measured concentrations of dapivirine in vaginal fluids

The secondary endpoints are:

- The HIV-1 seroconversion rate per 100 woman-years of product use at the end of the vaginal ring use period
- HIV-1 drug resistance mutations among participants who acquire HIV-1 infection

The secondary endpoints will be assessed through:

- Rapid and specialised laboratory testing according to a pre-specified HIV testing algorithm
- Viral genotype resistance testing methods

The exploratory endpoints are:

- Feasibility of 3-monthly clinical follow-up schedule
- Dapivirine residual amounts in returned used vaginal rings and/or dapivirine concentrations in blood and/or vaginal fluid in correlation with results from the visual inspection of the returned used vaginal rings by research staff
- Proportion of participants opting for HIV rapid tests at the research centre between scheduled 3-monthly research centre follow-up visits

The exploratory endpoints will be assessed through:

- Participant report of feasibility regarding a 3-monthly clinical follow-up schedule (Participant Questionnaire)
- Number of women opting not to receive two additional rings at the 3-monthly visits
- Proportion of returned rings (used and unused) during the 3-monthly clinical follow-up schedule
- Dapivirine residual amounts in returned used vaginal rings and/or dapivirine concentrations in blood and/or vaginal fluid
- Visual inspection of the returned used vaginal rings by research centre staff
- Number of participants undergoing HIV rapid tests at the research centres between scheduled 3-monthly research centre follow-up visits

3. Overall Trial Design

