3.3. Trial Population

Approximately 1400 HIV-negative women who have participated in the IPM 027 Phase III Dapivirine Vaginal Ring-004 trial, who understand the trial, and can provide informed consent are expected to enrol in this open-label trial.

3.3.1. *Inclusion Criteria*

Women must meet all the following criteria to be eligible to enrol in the trial:

1. Previously enrolled in the IPM 027 trial
2. Available for all visits and consent to follow all procedures scheduled for the trial
3. Using an effective method of contraception at the Enrolment Visit, and intending to use an effective contraceptive method for the duration of trial participation, unless post-menopausal with no history of menses for one year prior to screening
4. HIV-negative as determined by the HIV algorithm applied at Screening/Pre-Enrolment
5. Willing to refrain from participation in another research trial using drugs, vaccines, medical devices and microbicides for the duration of the IPM 032 trial
6. Willing to provide adequate locator information for trial retention purposes and be reachable per local standard procedures (e.g., by home visit or telephone; or via family or close neighbour contacts); confidentiality to be maintained

3.3.2. *Exclusion Criteria*

Women who meet any of the following criteria are NOT eligible to enrol in the trial:

1. Investigational product use permanently discontinued in response to an AE (where the AE was considered related to investigational product) or safety-related concern while taking part in the IPM 027 trial
2. Participant self-report of taking post-exposure prophylaxis (PEP) within ≤ 2 months at Screening Visit

Note: Participants may be enrolled after completing the PEP regimen and a negative HIV test was documented at least 2 months prior to screening for IPM 032

3. Currently pregnant, intends to become pregnant or currently breast-feeding
4. Known drug abuse or alcohol dependence in the 12 months prior to screening

5. Participated in another research trial (other than IPM 027) using drugs, medical devices, microbicides or oral pre-exposure prophylaxis agents within 30 days prior to screening
6. Any new illness or condition(s), chronic condition(s) or abnormal laboratory finding(s) that, in the opinion of the investigator, might put the participant at risk, or interfere with the trial objectives or the participant's adherence to trial requirements

4. Trial Visits and Procedures

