Centre 01: Madibeng Centre for Research (MCR); Centre 02: MatCH Research Unit (MRU); Centre 04: Qhakaza Mbokodo (QM);
Centre 06: MRC/UVRI & LSHTM Uganda Research Unit (MRC/UVRI); Centre 07: Desmond Tutu HIV Foundation (DTHF), Masiphumelele; Centre 08: Ndlovu Care Group (NCG)

Listing 16.2.8.6
Physical Examination
Safety Population

Centre Participant ID	Date of Exam	Visit	Body System or Part	Description of AE	IPM 027 Treatment	Comments
Centre XXX XXXXXXXX	ddMMMyyyy	Screening / Trial Month XX / Trial Month XX (Unscheduled X) / Exit visit	General appearance / Gastrointestinal/ Abdomen / Neck Lymph node / Cardiovascular/ Heart / Respiratory/Lungs / Neurological / Skin / Eyes / Ears, nose, throat / Other: XXXXXXXX		Dapivirine / Placebo	

AE = Adverse event; CRF = Case report form

Centre 01: Madibeng Centre for Research (MCR); Centre 02: MatCH Research Unit (MRU); Centre 04: Qhakaza Mbokodo (QM);
Centre 06: MRC/UVRI & LSHTM Uganda Research Unit (MRC/UVRI); Centre 07: Desmond Tutu HIV Foundation (DTHF), Masiphumelele; Centre 08: Ndlovu Care Group (NCG)

Listing 16.2.8.7
 Menses Information and Pregnancy Test Results
 Safety Population

Centre Participant ID	Collection Date	Visit	Menses Information			Pregnancy Test		
			N/A at Scheduled Visits	First Day of Last Menstrual Period	Changes to Menses from Previous Visit	Urine Test Result	Serum Collection Date	Serum Test Result
Centre XX XXXXXXXXX	ddMMMyyyy	Screening / Trial Month XX / Trial Month XX (Unscheduled X) / Exit visit	Yes	ddMMMyyyy / N/A	No / N/A / Yes: XXXXXXXXXXXX	Negative / Positive / Not done	ddMMMyyyy / N/A	Negative / Equivocal / positive

Programmers Note: Capture all methods used to estimate date of deliver, separated by ;

Centre 01: Madibeng Centre for Research (MCR); Centre 02: MatCH Research Unit (MRU); Centre 04: Qhakaza Mbokodo (QM);
 Centre 06: MRC/UVRI & LSHTM Uganda Research Unit (MRC/UVRI); Centre 07: Desmond Tutu HIV Foundation (DTHF), Masiphumelele; Centre 08: Ndlovu Care Group (NCG)

Listing 16.2.8.7
Menses Information and Pregnancy Test Results
Safety Population

Centre Participant ID	Collection Date	Visit	On Contraceptive at Positive Pregnancy Test: Name	Pregnancy Report	
				Estimated Day of Delivery	Information Used to Estimate Date of Delivery

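### The protocol's reporting exclusion for bleeding attributed to contraception has no grade limit, so non-serious Grade 3-4 bleeding can drop out of a primary safety endpoint that is meant to count every such event

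*Protocol*

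**What the plan says.** Protocol 7.1 defines an AE broadly and independently of cause, and says that all AEs will be recorded and graded. It then adds an exception: "A vaginal bleeding abnormality thought to be due to contraception, asymptomatic BV and asymptomatic candidiasis will not be reported as an AE for this trial". The restriction to asymptomatic cases applies to BV and candidiasis. Nothing comparable limits the bleeding part, and no criteria are given for deciding that contraception is the cause.

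Protocol 2.2 names three primary safety endpoints: "All Adverse Events (AEs) assessed by the investigator to be related to the Dapivirine Vaginal Ring-004", "All Grade 3 and 4 AEs", and all SAEs. SAP 2.4 repeats them. The second and third do not depend on cause.

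Protocol 3.3.1 requires each woman to be "Using an effective method of contraception at the Enrolment Visit, and intending to use an effective contraceptive method for the duration of trial participation", with post-menopausal women exempt. Section 5.5 repeats the requirement.

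SAP 10.1.2 (Table 2) takes the Grade 3-4, related and serious event counts from the AE form. SAP 10.1 gives its own AE definition without mentioning the 7.1 exception. SAP Appendix 5 groups amenorrhoea, menorrhagia, metrorrhagia and irregular menstruation as bleeding disorders among the events of special interest.

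**The concern.** A judgement about cause decides whether a bleeding event reaches the AE form at all. Grade and relation to the ring are recorded only on events that get that far. An endpoint described as covering all Grade 3-4 events, whatever their cause, therefore has a cause-based gap.

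The judgement is open to nearly every participant, because contraception is a condition of entry and of continued participation. It is made in an open-label trial with no concurrent control, so no comparison arm could reveal that events were being set aside.

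Bleeding also matters for this product. Protocol 1.4.1 lists metrorrhagia first among the common events in the completed Ring-004 trials, at 29.7% on dapivirine rings and 24.4% on placebo rings. A reader of the SAP's bleeding-disorder summaries would not know that events had been removed before coding.

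**Working it through.** The plan has no figure of its own on this point, so the check is mainly a comparison of sections.

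1. **Does any grade or seriousness limit apply to the exclusion?** None appears in 7.1. Section 7.2 sends genital complaints to the female genital grading table, but does not say that a high grade overrides the exclusion.

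2. **Is serious bleeding still reportable?** Section 7.4.1 defines an SAE in its own terms, as any untoward medical occurrence meeting a seriousness criterion, and requires all SAEs to be reported whether or not they are associated with the ring. Serious bleeding is therefore largely covered, although the protocol does not say which section prevails. The clear gap is bleeding that is Grade 3-4 but not serious.

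3. **Can an excluded event reach the Grade 3-4 endpoint by another route?**
   - Section 5.9 requires abnormal bleeding to be investigated. It does not require it to be reported.
   - Pelvic findings include abnormal genital tract bleeding (SAP Table 6), and the general section of Listing 16.2.8.16 has a grade column. Routine examinations take place only at screening and the last product use visit, and these data do not feed the endpoint.
   - Listing 16.2.8.7 has a column "Changes to Menses from Previous Visit". It carries no grade, and no table in the SAP's list summarises it.

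   None of these routes closes the gap.

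4. **Is the exclusion needed to keep unrelated bleeding out of the related-event endpoint?** No. Section 7.3 already lets the investigator class an event as not related when a concomitant medication explains it. That keeps the event, its grade and its attribution on record. The SAP otherwise leans the cautious way: under 10.1.2 a missing relationship counts as related and a missing severity counts as maximum.

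5. **How large could the omission be?** The two inputs needed are not in the documents, so both are assumptions:
   - N = 1400 (Protocol 8.3, approximate)
   - g, the true proportion of women with non-serious Grade 3-4 bleeding: 0.1% to 1% (assumed)
   - s, the share attributed to contraception: 25% to 90% (assumed)

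   Women left out = N × g × s
   - Low: 1400 × 0.001 × 0.25 = 0.35
   - Middle: 1400 × 0.005 × 0.50 = 3.5
   - High: 1400 × 0.01 × 0.90 = 12.6

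   As a shift in the endpoint proportion, g × s runs from 0.025 to 0.9 percentage points. This is an upper bound for each pair of values, because a woman with another Grade 3-4 event is counted anyway.

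6. **What do the earlier bleeding data show?** With "n=259 using dapivirine rings and n=160 using placebo rings", 0.297 × 259 ≈ 77 and 0.244 × 160 ≈ 39. Fisher's exact test on 77/259 against 39/160 gives p ≈ 0.26. Bleeding is common, but these data do not establish a ring effect.

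**The case against.** The strongest reply is that the exclusion is openly pre-specified, that serious bleeding is protected by 7.4.1, and that 5.9 obliges the site to look for a source before settling on contraception. Not every method offers a hormonal explanation: the contraceptive listing includes condoms and surgical sterilisation. Operational detail, possibly including a grade limit, may sit in the study operations manual or the genital grading table, which are not available here. Most of this stands, and it narrows the point. It does not remove it, because the protocol as written still lets non-serious Grade 3-4 bleeding go unreported.

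A reader might infer more than the documents support, in four ways.

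- **Hundreds of missing events.** Applying 29.7% to 1400 gives about 416 women (0.297 × 1400), and an assumed attribution share then gives a large count. That figure is metrorrhagia of any grade, so it does not measure the Grade 3-4 gap. Nor do the documents say whether the earlier trials already used a similar exclusion.
- **A hidden excess over placebo.** The earlier 5.3-point difference is compatible with chance, and a trial with no concurrent control could not show such an excess under any reporting rule.
- **An SAE endpoint that is compromised.** Section 7.4.1 mostly prevents this. What is missing is a statement of which section prevails.
- **Events lost for good.** Some bleeding remains visible in the menses and pelvic listings, although not in the endpoint.

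**Conclusion.** The point holds in a limited form. Followed as written, Protocol 7.1 allows non-serious Grade 3-4 bleeding attributed to contraception to be left out of a primary endpoint that is defined without regard to cause, and such events receive no recorded relatedness assessment. The bleeding-disorder summaries under SAP Appendix 5 are incomplete for the same reason, and the SAP does not disclose it.

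The direction is towards undercounting, but the documents do not show that the effect is material. The range of about 0.4 to 13 women rests wholly on assumed rates and shares. The conclusion also assumes that no document outside the protocol and SAP imposes a grade limit. The change is worth making because it brings the endpoint into line with its own definition at little cost.

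**What to change.** **Protocol.** Reconcile 7.1 with 2.2 and 7.4.1, and with SAP 10.1. Limit the reporting exclusion in 7.1 to non-serious Grade 1-2 bleeding, so that every Grade 3-4 or serious bleeding event is recorded as an AE with its attribution. The not-related category in 7.3 already accommodates events explained by contraception.

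**SAP.** State the exclusion in the AE definition and footnote it in the AE and bleeding-disorder tables. Add one table, by visit, of the menses changes already captured for Listing 16.2.8.7. If conduct is too advanced to change reporting, this part can still be done alone. It discloses the gap and gives some view of bleeding outside the AE data, but without grades it cannot restore the endpoint.

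**Cost.** One clause in the protocol, a few more AE forms, some footnotes and one table from data already collected. The Grade 3-4 proportion may come out slightly higher.

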7.2. Assessment of Adverse Event Severity

The investigator is responsible for assessing the severity of AEs occurring on trial. All AEs except genital complaints will be graded according to the latest version of the *DAIDS Table for Grading Severity of Adult and Pediatric Adverse Events*. All genital complaints will be graded according to the latest version of the *Female Genital Grading Table for Use in Microbicide Studies*, which will be provided to research centres in the SOM.

For AEs not listed on either of these tables, the following criteria will be used to estimate the grade of severity:

- **Mild**
Symptoms causing no or minimal interference with usual social and functional activities
- **Moderate**
Symptoms causing greater than minimal interference with usual social and functional activities
- **Severe**
Symptoms causing inability to perform usual social and functional activities
- **Potentially Life-threatening**
Symptoms causing inability to perform basic self-care functions OR medical or operative intervention indicated to prevent permanent impairment, persistent inability, or death

